3.8.2 Content of Control Group

Participants who are assigned to control group, they will be asked to fill in the questionnaire with the assistance of four facilitators (APPENDIX D) right away without any intended input given to participants. A briefing on how to answer the questionnaire will be given by main facilitator and all facilitators are allowed to answer any questions raised by respondents related to the questionnaire. However, they are not allowed to answer on behalf of the respondents. After the completion of the questionnaire, they will be informed about the subsequent follow up measurement after one, three and six month. After that, they will be dismissed and having usual care provided by the health clinic as before without any changes.

3.8.3 Facilitators and training

To conduct the KYM-TIFH, each session will require one (1) main facilitators and three (3) assistant facilitators to facilitate the program. A total of four (4) main facilitators and twelve (2) assistant facilitators to cater two study sites will be involved in the study. Besides, four qualified and trained facilitators are available for backup. As the number of participants for each sessions of the structured group based intervention is fixed between 20 to 24 participants, each facilitator will assist an average of 5-6 participants.

All the facilitators are the pharmacists who serve under the Pharmaceutical Services Division of Sarawak State Health Department. Facilitators who have experience of conducting at least two times of the intervention will be eligible as the facilitators for this study.

To ensure the consistency and correctness of facilitators in conducting the intervention according to the intervention content, three sessions of the interventions prior to the actual study will be

observed and assessed by the researchers on their performance in terms of coverage of all learning topics, consistency in conducting the intervention, communication with participants and responsiveness to participants' concerns using a structured report namely "Facilitator Competency and Inter-Coder Reliability Assessment Report" (APPENDIX F). All the aspects mentioned above are required to achieve 90%-100% in order to qualified as facilitators for this study. Moreover, among the qualified facilitators, facilitators who were trained to conduct Diabetic MTAC will be appointed as main supervisor. This is because the main facilitators need to have sufficient and up-to-date knowledge in addressing any medication-related-problems raised by participants during the KYM-TIFH. Nonetheless, to ensure the consistency and appropriateness in answering the questions related to the negative perceptions on medication, a booklet of frequently asked questions with answers will be provided to each facilitator and also to participants for their future reference (APPENDIX G).

Apart from training the facilitators to be familiar and consistent in conducting the intervention, the training of the facilitators also includes:

(1) learning how to eliminate concerns and questions the patients come across pertinent to medication adherence with mnemonic tool "ADHERE" adopted from Soto (2004).

- **Acknowledgement:** Acknowledge the concerns of patients.
- **Discuss:** Discuss with patients on their concerns.
- **Handle:** Handle concerns of patients promptly.
- **Evaluate:** Assess patients health literacy and identify possible barriers to adherence.
- **Recommend:** Suggest appropriate and feasible solution to the patient.

- Empower: Elicit patients' willingness to adhere with medications for long-term.

[figure not shown]
(2) learning what are the Dos and Don'ts when communicating with participants with guidelines provided by Gottlieb (2000):

- Adopt friendly attitude and not business-like attitude
- Avoid medical jargon
- Use short sentences
- Give clear instruction and repeat the instructions
- Give specific and detailed information
- Ensure the patients understand by asking them to repeat what had been said

(3) learning patient-centred communication as advocated by Jones (2004). It encourages the facilitators to be active listener and learn how to encourage the participants to think, understand about the problems about medication adherence they face and decide to act. It also involves nonverbal communication skills such as nodding and making eye contact to show genuine interest and concern on the issues raised by participants.

[figure not shown]
3.8.4 Setting of the venue

The setting of the venue for intervention group will be in 4 mini groups. The participants will be asked to count off from one to four in order to break them into the 4 mini groups, only then the intervention will begin. Besides, the four standing banners that aim to enhance the psychosocial variables towards medication adherence will be displayed. The setting of the venue for intervention group is illustrated in Figure 9 while for control group is illustrated in Figure 10.

☺ = Participant; ☹ = main facilitator; 😊 = assistant facilitator; Green rectangle = table

Figure 9: Setting of the venue for intervention group.

☺ = Participant; ☹ = main facilitator; 😊 = assistant facilitator

Figure 10: Setting of the venue for control group

3.8.5 Study Timeline

The researchers of this study will begin to screen and recruit respondents between 12nd to 23th June 2017. Besides, pre-test on the measurement scales will be conducted prior to actual data collection. The actual intervention will be on 17th to 21st July 2017 for HCKS and on 24th to 28th July 2017 for HCPJ. The post 1 month measurement of actual medication adherence will be carried out on 21st to 25th August 2017 for HCKS respondents and on 28th to 31st August 2017 for HCPJ respondents. The study timeline is illustrated as in Figure 11.

[figure not shown]

Figure 11: Time of interventions. MALMAS/IE: Medication Adherence Scale plus Inclusion & Exclusion Criteria Screening (Appendix A); TPB-IMB: Scale for Integrated Model of Theory of Planned Behaviour with Information-Motivation-Behavioural Skill Model (Appendix D); KYM-TIFH: “Know Your Medicine- Take if for Health” program; FGD/SI: Focus Group Discussion or Semi-Structured Interview; KS-HC: Kota Samarahan Health Clinic; PJ-HC: Petra Jaya Health Clinic

3.9 Outcome measurement

Primary outcome:

A validated 8-item Malay version of Medication Adherence Scale (MALMAS) will be employed to assess the level of medication adherence among Sarawak patients (Chung et al. 2015). All the items were translated into Bahasa Malaysia and were back translated to English by a group of four experienced language lecturers from University of Malaysia Sarawak.

Secondary outcome:

The psychosocial variables of Theory of Planned Behaviour and adherence information variable from IMB will be employed as secondary outcome of this study. The sources of the items to measure all the variables in conceptual framework are depicted in Table 4.

Paper-based questionnaires will be distributed to the targeted patients by trained enumerators during the group based intervention. Prior to answering the survey, subjects will be briefed about the structure of the questionnaire and how to answer the questions by main facilitator. Any enquiries raised by the respondents will be explained by facilitators.

Table 4: Instrument for the study

Variable	No. of items	Measuring scale	Adopted from
Adherence information	6	5 points Likert scale	McPherson et al. 2008
Attitude to adhere	5	5 points Likert scale	Farmer et al. 2006

Subjective Norm to adhere	6	5 points Likert scale	Farmer et al. 2006
Perceived Behavioural Control to adhere	11	5 points Likert scale	Fernandez et al. 2008
Intention to adhere	3	5 points Likert scale	Vissman et al 2013
Medication adherence	8	1-7 items are measured with binomial answers which are “yes” or “no”; the last item is measured with 5 points Likert scale	Chung et al. 2015
Demographic	15	(1) enrolled with diabetic MTAC; (2) numbers of medications, one or more than one; (3) frequency of the medications, a once-daily dose or more frequent; (4) age; (5) gender; (6) highest education level; (7) monthly household income; (8) employment status; (9) having complications; (10) taking traditional complementary and alternative medicines; (11) residential area, urban or rural; (12) living condition, having social support or stay individually; (13) undergone diabetic education by diabetic nurse; (14) newly diagnosed or established T2DM; (15) concurrent diseases	

3.10 Development of the questionnaire

All the items which are originally in English will be translated into Bahasa Malaysia and were back translated to English by a group of four experienced language lecturers from University of Malaysia Sarawak. Three experts in the field of behavioural studies will be invited to examine the content validity of the BM questionnaire. Furthermore, the translated questionnaire will be pre-tested by three Malay patients with T2DM from Sarawak General Hospital prior to the study. All comments given during pre-test pertinent to the questionnaire design, items and ease of administration will be reported and amendment will be conducted accordingly. The three individuals involved in pre-test would not be included in subsequent pilot and actual study. Subsequently, a pilot study to validate the questionnaire will be conducted by distribute the questionnaire to fifty (50) T2DM Malay patients from Sarawak General Hospital.

3.11 Data Analysis

The data analyses for this study will be comprised of validation of instrument, followed by data analyses to generate results for the three objectives of this study. The software that are essential to carried out the analyses will be IBM SPSS statistics (Version 21, IBM SPSS, Chicago, IL, USA) and SmartPLS 3 (Ringle et al. 2015).

3.11.1 Validation of instrument

Validity of the translated BM version of the instrument will be reported. Content validity will be examined prior to the actual study through three experts' opinion and pre-test. Principle Axis Factor Analysis with Bonferonni test with subsequent Cronbach's Alpha test will be carried out to test the construct validity. Discriminant and convergent validity will be examined using linear discriminant analysis and Pearson correlations respectively.

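### Linear discriminant analysis, the only named check of discriminant validity, cannot show that the five psychosocial scales are distinct; two further validation steps are misnamed

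*Protocol*

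**What the plan says.** Protocol section 3.11.1 assigns a procedure to each property of the translated questionnaire.

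- **Discriminant and convergent validity:** "Discriminant and convergent validity will be examined using linear discriminant analysis and Pearson correlations respectively".
- **Construct validity:** "Principle Axis Factor Analysis with Bonferonni test", followed by Cronbach's alpha.
- **Content validity:** three experts and a pre-test, before the study.

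Section 3.10 adds that "a pilot study to validate the questionnaire will be conducted by distribute the questionnaire to fifty (50) T2DM Malay patients". No derivation of the 50 is given. Section 3.11.1 does not say whether the factor analysis uses the pilot or the main-study data.

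Table 4 in section 3.9 gives the items per scale: "Adherence information 6 5 points Likert scale"; "Attitude to adhere 5 5 points Likert scale"; "Subjective Norm to adhere 6 5 points Likert scale"; "Perceived Behavioural Control to adhere 11 5 points Likert scale"; and three items for intention.

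The scales are then treated as separate quantities. In section 2.3, H2a to H2f posit separate relations for attitude, norm, control and intention, with information as a moderator, and H3a to H3e posit five separate group differences. Section 3.11.3 analyses the first set by PLS-SEM in SmartPLS 3. Section 3.11.4 analyses the second by t tests.

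**The concern.** Discriminant validity means that scales intended for different constructs do measure different things. Linear discriminant analysis addresses another question: which combination of variables best separates groups of persons known in advance. The similarity is in the name only. At most it could serve a known-groups comparison, and the protocol defines no groups.

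Two other labels in the section do not fit their task. A Bonferroni procedure adjusts for multiple testing and says nothing about whether items can be factored. Cronbach's alpha describes internal consistency, and two scales that overlap completely can both have a high alpha.

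The protocol's own theory makes overlap plausible. Section 2.2.2.1 allows perceived behavioural control to reflect internal factors, information among them. Yet H2c and H2d concern control, H2f concerns information, and H3c and H3e report an effect on each. If the translated scales overlap, the separate paths and effects cannot be read as separate.

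**Working it through.** **1. Method against property**

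| Property in 3.11.1 | Procedure named | What the procedure shows |
|---|---|---|
| Discriminant validity | Linear discriminant analysis | Separation of predefined groups of people |
| Convergent validity | Pearson correlations | Association between scores; no comparator is named |
| Construct validity | Principal axis factoring | Relevant: shows item grouping and cross-loading |
| Construct validity | Bonferroni step | Multiplicity correction; no role here |
| Construct validity | Cronbach's alpha | Internal consistency (reliability) |

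**2. Why alpha and raw correlations do not replace the missing check**

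The protocol gives no loadings, so I assume a common loading λ from 0.5 to 0.8. Suppose the 5 attitude and 6 norm items all reflect one single factor, that is, complete overlap. Every inter-item correlation is then λ². For a scale of k items, alpha = kλ² / [1 + (k − 1)λ²]. The correlation between the two scale scores is √(alpha₅ × alpha₆).

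At λ = 0.6, λ² = 0.36:
- alpha₅ = 1.80/2.44 = 0.74
- alpha₆ = 2.16/2.80 = 0.77
- correlation between scores = √(0.738 × 0.771) = 0.75

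| λ | alpha, 5 items | alpha, 6 items | Correlation of scores |
|---|---|---|---|
| 0.5 | 0.63 | 0.67 | 0.65 |
| 0.6 | 0.74 | 0.77 | 0.75 |
| 0.7 | 0.83 | 0.85 | 0.84 |
| 0.8 | 0.90 | 0.91 | 0.91 |

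Alpha rises with λ although the scales are identical in content. The raw correlation stays below 1 because of unreliability. The heterotrait-monotrait ratio divides the mean between-scale item correlation by the geometric mean of the within-scale ones. Here that is λ²/λ² = 1 at every λ, so it shows the overlap directly.

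**3. The pilot**

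The protocol gives no formula behind the 50, so there is no figure to reproduce. Items: 6 + 5 + 6 + 11 + 3 = 31. Ratio: 50/31 = 1.6 patients per item.

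Precision at n = 50:
- Correlation between scales, by Fisher's z (standard error 1/√47 = 0.146): an observed 0.50 has a 95% interval of 0.26 to 0.68; an observed 0.70 has 0.52 to 0.82.
- Alpha, by Feldt's F interval: an observed 0.70 has 0.52 to 0.82 with 3 items and 0.56 to 0.81 with 11.

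Factor recovery was simulated with normal items on five factors (6/5/6/11/3), principal axis factoring with the true number of factors, varimax rotation, and 300 runs per setting. The table gives the share of runs with all 31 items on the right factor, for factor correlations 0 / 0.3 / 0.5. The comparison n = 221 is the per-group minimum in section 3.7.

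| Loading | n = 50 | n = 221 |
|---|---|---|
| 0.5 | 0% / 0% / 0% | 99% / 81% / 24% |
| 0.6 | 33% / 9% / 1% | 100% / 99% / 92% |
| 0.7 | 95% / 72% / 31% | 100% / 100% / 100% |
| 0.8 | 100% / 97% / 89% | 100% / 100% / 100% |

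**The case against.** A reader might infer that the constructs stay unverified, or that the planned checks could not detect overlap. The documents do not support that. Principal axis factoring can show cross-loading or merged factors, Pearson correlations run between scales would show strong overlap, and experts review the content. The items are also adopted from published instruments. This evidence is partial but real.

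A reader might also take the factor analysis to rest on the 50 pilot patients. Section 3.10 makes that plausible, but section 3.11.1 does not say so. It places only content validity before the study, and section 3.11 lists instrument validation among the study's own analyses. What stands is that the dataset is not named.

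Three further inferences fail.

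- The 442 in section 3.7 is not a count of baseline questionnaires. It is an enrolment target already raised for 30% dropout or incomplete data. That leaves about 442 × 0.7 = 309 or 442/1.3 = 340 complete records.
- The interval for a correlation of 0.40 in 50 people (0.14 to 0.61) does not carry over to a rotated factor loading, so it cannot settle a loading cut-off.
- The pilot should not be cut back to wording and alpha. The Gantt chart schedules instrument revision for June and July 2017, and early structural evidence from the pilot is useful for it.

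Finally, cut-offs and measurement-model reporting are commonly left to an analysis plan, which is not shown here. That is fair for the cut-offs. It does not excuse naming in the protocol a method that answers a different question.

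**Conclusion.** The point holds in a limited form. The one procedure named for discriminant validity does not test it. The Bonferroni step is misnamed or misapplied; that Bartlett's test was meant is my inference. Alpha is filed under the wrong property.

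The consequence is an avoidable gap in the evidence that five scales are distinct, on which the paths of objective 2 and the five effects of objective 3 depend. It is not a demonstration that they overlap.

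How far 50 patients suffice depends on loadings that the documents do not give. Under the simulation's assumptions 50 is too few at loadings of 0.5 to 0.6, mixed at 0.7, and adequate at 0.8.

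This is a minor correction. It touches secondary outcomes and the model objective only. The primary MALMAS outcome, which the protocol describes as already validated in Malaysian patients with type 2 diabetes, is not affected.

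**What to change.** Amend section 3.11.1 as follows.

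- Replace linear discriminant analysis with the heterotrait-monotrait ratio or the Fornell-Larcker criterion, and use average variance extracted for convergent validity. Both can come from SmartPLS 3, which section 3.11 already names. Cut-offs can go in the analysis plan.
- Replace the Bonferroni step with Bartlett's test of sphericity, reported with the KMO measure.
- Report Cronbach's alpha as reliability.
- Keep the 50-patient pilot, including its factor analysis, as a preliminary check that can inform instrument revision.
- State that factor structure and discriminant validity will be confirmed on the trial's pre-session questionnaires: the form completed before the session in the intervention group (Table 3) and the control group's questionnaire (section 3.8.2). Answers given after the session would carry the intervention effect.

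The cost is a few sentences and some routine output. That output includes one extra measurement-model run, since objective 2 itself is assessed at the end of the trial. No patients are added. There are two small drawbacks: confirmation comes only after baseline collection, and the sample is restricted to patients with MALMAS below 6.

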3.11.2 Data analysis for first objective

The first objective of this study is to measure the effectiveness of the intervention in improving medication adherence. Descriptive statistics will be used to present the results on the level of medication adherence before and after the intervention. Mann-Whitney U test will be used to examine the change of patients between adherent patients (MALMAS > 6) and non-adherent patients (MALMAS < 6) before and after the intervention within same group. In terms of inter-group comparison for the medication adherence level (adherent vs non-adherent) before and after the intervention, Wilcoxon signed-rank will be executed.

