2.3 Hypotheses

Based on the first specific objective, two hypotheses to be tested are:

H1a: There is significant difference of medication adherence level among participants before and after the intervention.

H1b: There is significant difference of medication adherence level after the intervention between participants from intervention group and control group.

Based on the second specific objective, six hypotheses to be tested are:

H2a: There is a significant relationship between attitude to adherence and intention to adhere.

H2b: There is a significant relationship between subjective norm to adherence and intention to adhere.

H2c: There is a significant relationship between perceived behavior control to adherence and intention to adhere.

H2d: There is a significant relationship between perceived behavior control to adherence and medication adherence.

H2e: There is a significant relationship between intention to adherence and medication adherence.

H2f: There is a moderating effect by adherence information between intention to adhere and medication adherence.

Based on the third specific objective, five hypotheses to be tested are:

H3a: There is significant difference of attitude to adhere after the intervention between participants from intervention group and control group.

H3b: There is significant difference of subjective norm to adhere after the intervention between participants from intervention group and control group.

H3c: There is significant difference of perceived behavioural control to adhere after the intervention between participants from intervention group and control group.

H3d: There is significant difference of intention to adhere after the intervention between participants from intervention group and control group.

H3e: There is significant difference of adherence information after the intervention between participants from intervention group and control group.

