3.4.1 Inclusion Criteria

- i. 8 items MALMAS score < 6 (patients with middle and low adherence)
- ii. Malay patients > 18 years old

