3.5 Recruitment

A sampling frame that include all T2DM Malay patients who obtained the supply of the medications from the two study sites (HCKS and HCPJ) for more than three months, is obtained prior to the study. The method of obtaining sampling frame is done through screening all the prescriptions prescribed by the medical specialists, medical officers or health officers from both study sites within the period of 1st February 2017 to 30th April 2017. Information that could be obtained through prescription screening include the diagnosis and medications of the patients, name and age. Malay patients could be identified based on their name, with male having the word

“bin” or “b” and female having the word “binti” or ‘bt’ among their name characters. However, the exact ethnicity of the respondents will be confirmed in subsequent screening. As such, all potential respondents who are Malay T2DM patients will be approached during the screening phase.

After that, approximately one month prior to the actual study which is during 1st – 30th June 2017 (T0 screening), will be the screening phase to identify potential respondents for this study with structured screening form as in Appendix A. An 8-items MALMAS medication adherence scale that had been validated among Malaysian with T2DM (Chung et al. 2015), will be administered to obtain the adherence score which enable the researchers to evaluate the eligibility of the prospective respondents. Patients who are having middle and low medication adherence level (MALMAS score < 6) and fulfill all the inclusion and exclusion criteria will be provided with informed consent and study information sheet (APPENDIX B). Those who agree to participate will be informed about the KYM-TIFH and they will be asked to choose a date during the campaign to attend the program. After they choose the date they prefer, their name will be recorded in the “List of Participants” (APPENDIX C) with a specific code assigned. Notably, patients are not informed of their group assignment and thus are not aware of the differences between intervention group and control group. Besides, none of the recruiters who are the pharmacist staff at both health clinics, are aware of subsequent treatment allocation throughout the recruitment stage, to ensure allocation concealment. All research materials that contain patients’ information will be coded and kept by principal investigator to maintain confidentiality of respondents.

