3.7 Sample size

We are planning a study of a continuous response variable from independent control and experimental subjects with 1 control per experimental subject. In a previous study (Butt et al. 2016), the response within each subject group was normally distributed with standard deviation 1.8. If the true difference in the experimental and control means is 1, we will need to study 69 experimental subjects and 69 control subjects to be able to reject the null hypothesis that the population means of the experimental and control groups are equal with probability (power) 0.9 (Dupont and Plummer 1998). By estimating 30% of dropout or incomplete data, a minimum sample size 180 with 90 for both groups are pre-determined for each study sites.

On the other hand, to test the integrated model as mentioned in second objective, with effect size f square equal to 0.15, α error probability equals to 0.05, power equals to 0.95 and total number of predictors equal to 3, total sample size required will be 170 (Faul et al 2009). Assuming 30% of dropout or incomplete data, a minimum sample size 221. As a result, a total minimum sample size of 442 with 221 for both groups are acquired.

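### A MALMAS score of exactly 6 has no outcome class, and the 90% power is for a difference in means while the planned comparison is adherent versus non-adherent

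*Protocol*

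**What the plan says.** Section 3.11.2 splits patients into "adherent patients (MALMAS > 6) and non-adherent patients (MALMAS < 6) before and after the intervention within same group". It then makes the "inter-group comparison for the medication adherence level (adherent vs non-adherent) before and after the intervention", so the only between-arm comparison described for objective 1 uses the dichotomy. Hypothesis H1b in section 2.3 and the primary outcome in section 3.9 refer only to the level of adherence. Neither settles whether the score or the class is meant.

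The entry rule uses the same cut. Section 3.4.1 has "8 items MALMAS score < 6 (patients with middle and low adherence", and section 3.5 repeats it: "Patients who are having middle and low medication adherence level (MALMAS score < 6".

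The sample size in section 3.7 rests on something else: "We are planning a study of a continuous response variable from independent control and experimental subjects". With an SD of 1.8 it continues: "If the true difference in the experimental and control means is 1, we will need to study 69 experimental subjects and 69 control subjects", for power of 0.9. The section does not name the scale behind the SD and gives no adherent proportions. After a separate calculation for objective 2 it ends with "a total minimum sample size of 442 with 221 for both groups are acquired".

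**The concern.** There are two faults, both in how the primary comparison is fixed.

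- **The boundary.** Everyone enters with a score below 6, so on a whole-number scale 6 is the first value at which a patient leaves the entry range. That is where improvement would be counted, and it is the one value without a class. If its place is settled after follow-up data are seen, the reported adherence rates are open to choice.
- **The basis of the power.** The 90% belongs to a test of means that section 3.11.2 does not name. Cutting a score in two discards information, so the same one-point shift is harder to detect on the dichotomy, and nothing in the protocol shows what power the dichotomy has.

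**Working it through.** **Inputs from the protocol:** difference in means 1, SD 1.8, power 0.90, 1:1 allocation, 69 per group, 30% dropout, final 221 per group (all section 3.7); cut at 6 (section 3.11.2); seven yes/no items and one 5-point item (section 3.9, Table 4).

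**Assumptions:** two-sided alpha 0.05 for objective 1 (section 3.7 states 0.05 only for the model calculation); the response in 3.7 is MALMAS; follow-up scores are normal with SD 1.8 and a shift of 1 between arms; the control mean at follow-up, which the protocol does not give, is varied from 3 to 6. The scoring key is not in the protocol. A total of 6 is attainable if the yes/no items score 0 or 1.

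**1. The plan's own figure.** n per group = 2(z0.975 + z0.90)²·SD²/difference² = 2 × (1.960 + 1.282)² × 1.8² / 1² ≈ 68.1, so 69. Noncentral-t power at 69 is 0.8997. The figure reproduces as a two-sided 5% test of means.

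**2. The same shift on the dichotomy.** To isolate the power question, treat the score as continuous and classify everyone by a cut at 6. The adherent share is p = 1 − Φ((6 − mean)/1.8). Power for two proportions, with pooled variance under the null, is

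Φ( [ |pE − pC|·√n − z0.975·√(2p̄(1 − p̄)) ] / √(pC(1 − pC) + pE(1 − pE)) ).

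At control mean 4, pC = 0.133, pE = 0.289 and p̄ = 0.211. With n = 69 this is Φ((1.296 − 1.132)/0.567) = Φ(0.29) = 0.61.

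Completers at the final size: 221 × 0.7 = 154.7, taken as 154.

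| Control mean | Adherent, control vs intervention | Power, 69 per group | n per group for 90% | Power, 154 per group |
|---|---|---|---|---|
| 3 | 5% vs 13% | 0.42 | 235 | 0.75 |
| 4 | 13% vs 29% | 0.61 | 142 | 0.92 |
| 5 | 29% vs 50% | 0.72 | 111 | 0.97 |
| 5.5 | 39% vs 61% | 0.73 | 108 | 0.97 |
| 6 | 50% vs 71% | 0.72 | 111 | 0.97 |

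The test of means has 0.900 at 69 per group and 0.998 at 154.

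**3. How many score exactly 6.** With whole-number scores, take the normal mass between 5.5 and 6.5. For arm means 4, 5, 6 and 7 this is 0.120, 0.188, 0.219 and 0.188, or about 18 to 34 of 154 completers per arm. If item 8 adds quarter steps, the mass between 5.875 and 6.125 is 0.030 to 0.055, or about 5 to 9 of 154.

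**4. What the choice does to the result.** Whole-number scores, control mean 4, intervention mean 5:

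| Rule for a 6 | Control | Intervention | Difference | Odds ratio |
|---|---|---|---|---|
| Not adherent (adherent is > 6) | 8.2% | 20.2% | 12 points | 2.8 |
| Adherent (adherent is ≥ 6) | 20.2% | 39.1% | 19 points | 2.5 |
| Dropped | 9.4% | 24.9% | 16 points | 3.2 |

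The dropped row divides by those left: 0.082/(1 − 0.120) and 0.202/(1 − 0.188). Power at 154 per arm over control means 4 to 6 is 0.86-0.97, 0.95-0.97 and 0.92-0.99 under the three rules.

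**The case against.** The strongest reply is that the gap is loose notation with an obvious answer. The protocol handles age the same way: inclusion is above 18, exclusion is below 18, and exactly 18 is left out. Since scores below 6 are called middle and low, 6 and above is the natural remaining level. That supports reading the rule as ≥ 6, but it does not fix it. Classing 6 as non-adherent is an equally small edit and gives different rates.

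The second reply is that the power mismatch has little consequence. The 61-73% applies to 69 per group, while the plan ends at 221 per group, where the dichotomy has at least 92% power unless the control mean is very low. This stands, and it limits the weight of the point. However, 221 comes from the objective 2 model calculation, so its adequacy for the dichotomy is incidental and nowhere shown.

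The third reply is that the sizes are modelled, and this also stands. An unbounded normal fits poorly near the top of the scale: if the maximum is 8, about 29% of the curve lies above it at a mean of 7. The quarter-step share is only a rough illustration, because a fractional item 8 gives a total of exactly 6 only when it contributes 0 or 1. The odds ratio also moves less than the rates do. Finally, the power shown is for a two-proportion test, not for the Wilcoxon signed-rank test that 3.11.2 names between groups; that choice of test is a separate matter.

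**Conclusion.** Both parts hold on the text. A score of 6 has no outcome class, and the 90% in section 3.7 describes a comparison of means that section 3.11.2 does not make.

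Under the stated assumptions, the boundary could affect 12-22% of follow-up scores on a whole-number scale, fewer with fractional scoring. At a control mean of 4 it moves the difference in adherence rates between 12 and 19 points. At the size section 3.7 gives for objective 1, the dichotomy has 61-73% power for control means of 4-6 (42% at 3) and would need 108-142 per group (235 at 3).

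At the final size with 30% loss, power is 92-97% (75% at a control mean of 3). This is therefore an undefined class plus a mismatch of basis and a loss of efficiency, not an underpowered trial. It should be fixed before follow-up data are analysed. The wording is certain; the magnitudes depend on the assumed score distribution and on the response in 3.7 being MALMAS.

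**What to change.** In section 3.11.2:

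- Define adherent as MALMAS ≥ 6, the complement of the entry rule, and state how the items are scored.
- Make the between-arm test of H1b a comparison of the continuous MALMAS score, adjusted for the screening (T0) score and site. This matches section 3.7 and uses data already collected.
- Keep adherent versus non-adherent as a secondary comparison.

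If the dichotomy is to remain primary, restate the power in section 3.7 for a difference in proportions at the final sample size, with the assumed control rate. In either case, name the scale to which the SD of 1.8 refers.

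The cost is small: a one-character change to the boundary and a short edit to 3.11.2 or 3.7, with no new data. The drawback of the continuous primary is that the headline result becomes a score difference, with the percentage adherent reported second.
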